10.0 Procedures Involved

10.1 Provide a description of all research procedures or activities being performed and when they are performed once a subject is screened and determined to be eligible. Provide as much detail as possible.

NOTE: This should serve as a blueprint for your study and include enough detail so that another investigator could pick up your protocol and replicate the research. For studies that have multiple or complex visits or procedures, consider the addition of a schedule of events table in in your response.

Response:

Randomization of subject into one of the three study arms

There will be three arms of this study with each arm testing a different pain reducer: Buzzy Bee, Vapocoolant, and placebo. We will use a sham device e.g. a band around the arm for placebo control.

After obtaining informed consent, the patients will be randomized into one of the three groups following a randomization table created by a statistician. Whichever intervention is randomly selected will be performed on patient prior to the needle stick.

These methods have been used in the ED as part of routine procedures to help patient for pain relief from a needle stick, the RNs are familiar with these methods. However, for the purpose of this study, the training videos will be uploaded in the Kaleidoscope Talent management for RNs to review the procedure and help them to refresh their memories.

Videotaping of subject

Using a camera, an ED research assistant will videotape subject's whole body including the facial expression while phlebotomy and IV catheter placement is performed for scoring of the PBCL. We will tape the entire venipuncture procedure starting from sterilization and ending at the time when the venipuncture is completed. If the first venipuncture procedure attempt is failed, we will not tape the second attempt. This subject will be withdrawn from the study.

Obtaining pain scores from subject and legal guardian using the Faces Pain Scale-Revised instrument

Before and after the venipuncture procedure, we will ask the legal guardian and subject to complete a Faces pain scale revised form. Since the revised form is validated to use for both adult and children, the same document will be used for the legal guardian and children for this study. This document is attached with this submission.

Reviewing of the videotape

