Two physicians will review the video tape independently, and give a score using the PBCL tool. These two physicians are blinded to the study aims. They will be trained on how to use the PBCL by the PI.

In the event when there is a discrepancy of the PBCL score between the two reviewers, the mean of the two scores will be used as the final score.

10.2 Describe what data will be collected.

NOTE: For studies with multiple data collection points or long-term follow up, consider the addition of a schedule or table in your response.

Response:

We will collect demographic data, reason for venipuncture, PBCL score, facial pain score etc.

10.3 List any instruments or measurement tools used to collect data (e.g. questionnaire, interview guide, validated instrument, data collection form).

Include copies of these documents with your submission.

Response:

The following documents will be used for data collection:

1. Data collection form

2. Procedure behavior check list (PBCL)
3. The Faces Pain scale-revised document.

These documents will be submitted with this IRB application.

10.4 Describe any source records that will be used to collect data about subjects (e.g. school records, electronic medical records).

Response:

Kaleida health Electronic power chart records will be used for data collection.

*10.5 Indicate whether or not **individual** subject results, such as results of investigational diagnostic tests, genetic tests, or incidental findings will be shared with subjects or others (e.g., the subject's primary care physician) and if so, describe how these will be shared.*

Response:

No individual subject results will be shared with the subject or others.

*10.6 Indicate whether or not **study** results will be shared with subjects or others, and if so, describe how these will be shared.*

Response:

Study results will not be shared with subjects or others. The final results of this study may be presented at a conference or published in a peer reviewed journal; however, only group data will be publicized in these circumstances, no individual identifiable information will be released.

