The research assistants work 7 days a week, 13 hours per day enrolling patients. The PI will work 1-2 hours per week to address questions related with the study. The two reviewers will work for about 2 hours per week to review the video tape.

14.3 Describe the availability of medical or psychological resources that subjects might need as a result of anticipated consequences of the human research, if applicable.

NOTE: One example includes: on-call availability of a counselor or psychologist for a study that screens subjects for depression.

Response:

This study involves minimum risk to the participant. We will videotape participant's whole body during the needle stick process. We do not anticipate any consequences related with the videotaping procedure.

14.4 Describe your process to ensure that all persons assisting with the research are adequately informed about the protocol, the research procedures, and their duties and functions.

Response:

The PI, mentors and the study coordinator have involved in the development of the study protocol, they are very familiar with the study design and their duties and functions.

The Research assistants will directly work under the supervision of the study coordinator. The RAs' duties will include: screening potential eligible patient, obtaining consent/assent, videotaping patient and legal guardian as well as collecting data on data collection form.

The study coordinator will provide training to all RAs before the RAs start patient's recruitment. The training is focused on the following aspects:

1. Review study protocol by presenting the materials to the RAs with a slide show. The RAs are required to understand the study aims/purpose and the detail of the study procedures.
2. Review data collection forms. The RAs are required to know the inclusion and exclusion criteria for the study and know what kinds of patients are potentially eligible and need to be screened for the study. In addition, they will also be trained on how to collect data on the data collection form.
3. Review the consent documents. The RAs are required to know (a) the contents of the consent documents, (b) how to approach and introduce the study to the legal guardian and patient (c) how to address some of the common questions that the patient may have (d) immediately contact the study coordinator or PI for a question to which they do not know the answer.

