17.0 Data Management and Analysis

17.1 *Describe the data analysis plan, including any statistical procedures. This section applies to both quantitative and qualitative analysis.*

Response:

All data analyses will be performed with SAS (version 9.2; SAS Institute, Inc., Cary, NC) and R (version 3.0.3) software. Chi-square and Fisher's exact test will be used to compare adverse events (e.g., systemic reaction, anaphylaxis, SOB, dyspnea, excess bleeding or hematoma formation), venipuncture and catheterization first attempt success, and number of patients with no to mild pain during needle insertion.

The Kruskal-Wallis test will be used to compare each of the two observers' assigned scores on the PBCL across three time periods: pre, procedure and post-procedure. Pre-procedure is defined as the time period prior to needle insertion including the placement of Vapocoolant, pain control or sham device up to needle insertion. The procedure period is defined as needle insertion through withdrawal. Post-procedure is defined as the 2 minute time period after needle withdrawal. Only patient and observer pain scores will be used for first-time needle insertion. If first attempt is failed, subject will be withdrawn from the study. Comparisons of pain scores of the five intervention groups to placebo (sham device) will be analyzed via ANOVA.

17.2 If applicable, provide a power analysis.

NOTE: This may not apply to certain types of studies, including chart/records reviews, survey studies, or observational studies. This question is asked to elicit whether the investigator has an adequate sample size to achieve the study objectives and justify a conclusion.

Response:

For chi-square analysis, based on a medium effect size of 0.3, alpha of 0.05, degree of freedom of 8, and 80% power it is estimated we will need a total of 168 subjects (56 per group). (*QFAB Bioinformatics*. 2015)

17.3 Describe any procedures that will be used for quality control of collected data.

Response:

Our RA will double check the data form to assure accuracy and completeness of data collection, if there is any missed data point, the RA will fill in the missing information immediately.

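### Taping stops when the venipuncture is completed, but the analysis needs PBCL scores for the two minutes after needle withdrawal

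*Combined protocol and SAP*

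**What the plan says.** Recording. Section 10.1 has a research assistant film the child's "whole body including the facial expression while phlebotomy and IV catheter placement is performed for scoring of the PBCL". The window is explicit: "We will tape the entire venipuncture procedure starting from sterilization and ending at the time when the venipuncture is completed". Section 14.3 describes the same recording as covering the child's "whole body during the needle stick process".

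Scoring. Section 10.1 continues: "Two physicians will review the video tape independently, and give a score using the PBCL tool". Section 18.1 A has the observers work from the stored file at their offices, and Section 18.3 A gives them access to the video data. No bedside PBCL scoring is described.

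Analysis. Section 17.1, and the identical text after Section 32.0, states: "The Kruskal-Wallis test will be used to compare each of the two observers", and continues with their "assigned scores on the PBCL across three time periods: pre, procedure and post-procedure". Two of the definitions matter here: "The procedure period is defined as needle insertion through withdrawal" and "Post-procedure is defined as the 2 minute time period after needle withdrawal".

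**The concern.** The last analysis period begins at about the moment when the camera is told to stop. Research assistants trained on the protocol and following it exactly would not be expected to film the two minutes that Section 17.1 defines as post-procedure. Footage that was not taken cannot be recovered, and Section 11.2 rules out follow-up, so the gap cannot be closed at the analysis stage.

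If the observers instead scored whatever footage happened to follow withdrawal, its length would be uncontrolled. Section 3.1 describes the PBCL as rating frequency as well as intensity of behavior, so scores from post-procedure clips of different length may not be comparable. At stake is one of the three pre-specified PBCL periods.

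**Working it through.** The plan states no figure on this point. The check compares time windows and then counts scores.

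**1. Windows side by side**

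- Taping (10.1): sterilization to completion of the venipuncture.
- Taping (14.3): the needle stick.
- Procedure period (17.1): needle insertion to withdrawal. This lies inside the taped window.
- Post-procedure period (17.1): withdrawal to two minutes later. No section provides for taping it.

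If completion means needle withdrawal, 0 of the 2 minutes are on tape. If completion is later, for example once a catheter is secured, some of the two minutes may be caught. The term is not defined, so the amount is unknown and may differ between phlebotomy and IV placement.

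**2. Other sources for those two minutes**

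The activity described after the procedure is the Faces Pain Scale – Revised form for child and guardian (10.1). Its completion by the child ends participation (11.2). It is a different instrument and supplies no PBCL score.

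**3. Scores at risk**

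Inputs: 168 subjects (5.1), two observers and three periods (17.1).

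- All observer-by-period scores: 168 × 2 × 3 = 1,008.
- Post-procedure scores: 168 × 2 = 336.
- Share: 336 / 1,008 = 33.3%.
- If the two observers' scores are averaged (10.1): 168 of 168 × 3 = 504, again 33.3%.

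The counts are upper limits, because subjects with a failed first attempt are withdrawn (10.1, 20.1). The share does not change. Both calculations assume a separate score for each period, which only Section 17.1 implies. Sections 10.1 and 18.1 A read as one score per observer for each subject, and on that reading the one-third figure does not apply.

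**4. Cost of filming two more minutes**

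- Footage: 168 × 2 / 60 = 5.6 hours.
- Two reviewers: 5.6 × 2 = 11.2 reviewer-hours.
- Review time stated in 14.2: about 2 hours per week. Over 24 months of recruitment (11.1), about 104 weeks, this is 208 hours if the 2 hours are shared, or 416 if they are per reviewer.
- Share of review time: 11.2 / 208 = 5.4%, or 11.2 / 416 = 2.7%.
- Section 11.3 also gives a total duration of 16 months, which does not fit 24 months of recruitment. On 16 × 52 / 12 = 69.3 weeks the shares would be 11.2 / 138.7 = 8.1% and 11.2 / 277.3 = 4.0%.

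**The case against.** The strongest reply is that little of importance depends on this period. Section 1.1 states the purpose in terms of anxiety and pain during venipuncture, and Section 2.1 names no post-procedure outcome. The PBCL over the needle stick itself and the child and guardian Faces scores are still collected. This stands, and it limits the severity.

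A second reply is that *completed* may be read generously, or that staff would keep filming anyway. The first part stands to the extent that some post-withdrawal footage may exist. Neither part supplies the two minutes: the amount is unspecified and no section tells staff to continue.

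A third reply is that varying clip length is not peculiar to this period, since the time from insertion to withdrawal also varies between children. That is fair. The difference is that the post-procedure period is defined by a fixed length, which the recording instruction does not deliver.

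A reader might also infer losses in the test itself, such as a Kruskal-Wallis test reduced from three groups to two, or lost contrasts between pairs of periods. The documents do not support stating these as damage to the plan. They do not settle whether the test compares periods or compares arms within each period, and they plan no pairwise period contrasts.

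**Conclusion.** The recording instruction and the analysis plan contradict each other, and this should be fixed. Followed as written, the plan gives no assured post-procedure PBCL for any subject. Up to 336 of 1,008 observer-by-period scores (one third) are at risk if each observer scores each period. The conclusion rests on the video being the only PBCL source described. The PBCL form and data collection form were not available for this review. They could show how periods are scored, but a scoring form cannot supply footage.

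Three stronger readings go too far:

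- That the trial's main comparison is compromised. The post-procedure period is never designated primary, and no effect on the ANOVA against placebo is shown.
- That all post-procedure footage is certain to be missing. Because *completed* is undefined, the supportable statement is that none is assured.
- That the pre-procedure period is lost too. Section 17.1 puts placement of the intervention inside that period and taping starts at sterilization, but the documents do not say which comes first. That is a separate point to clarify, not a shown error.

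**What to change.** Preferred: amend Section 10.1 so that taping ends two minutes after needle withdrawal, in all arms. Then align the two sections that would otherwise still conflict:

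- Section 14.3: describe the taping window in the same terms.
- Section 11.2: allow for the added time in the stated 5–10 minutes, and say whether the after-procedure Faces form is completed during or after the two minutes.

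The cost is protocol wording and two more minutes of recording per child by the same research assistant. That is about 5.6 hours of footage and 11 reviewer-hours in total, or 2.7–5.4% of the stated review time over 24 months. Participation lengthens by at most two minutes (2/10 to 2/5 of the stated duration). Extending the end of taping does not require filming the application of the intervention.

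Alternative: leave taping as it is, delete the post-procedure period from both Section 17.1 and the repeated text after Section 32.0, and report that no post-procedure PBCL comparison is made. This adds no recording but gives up that comparison.

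In either case, confirm against the PBCL form that observers score each period separately. As a separate clarification, state whether the intervention is placed before or after sterilization.

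### Taping starts at sterilization, but the scored PBCL pre-period includes placement of the intervention and has no stated start, so placement before skin cleaning would be scored without footage

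*Combined protocol and SAP*

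**What the plan says.** **Recording (10.1).** "We will tape the entire venipuncture procedure starting from sterilization", and "ending at the time when the venipuncture is completed".

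**Scoring (10.1, 18.1 A).** Two physicians score the PBCL from the video. No live or off-video scoring is described.

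**Analysis (17.1, repeated word for word after section 32).** The Kruskal-Wallis test compares "scores on the PBCL across three time periods: pre, procedure and post-procedure". The pre-procedure period is "the time period prior to needle insertion including the placement of Vapocoolant, pain control or sham device up to needle insertion".

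**Timing of the intervention (10.1).** The only rule is "Whichever intervention is randomly selected will be performed on patient prior to the needle stick". Its order relative to skin cleaning is not given for any arm.

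**Self-report and guardian report (10.1).** "Before and after the venipuncture procedure, we will ask the legal guardian and subject to complete a Faces pain scale revised form". Nothing ties the first form to randomization or to application of the intervention.

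**The concern.** The camera rule and the scoring rule are anchored to different events. The camera waits for sterilization. The scored pre-period must contain placement, which may come earlier. Where it does, the physicians are asked to score behavior they cannot see, and footage that was never taken cannot be recovered.

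A loss equal across arms would only weaken the pre-period score. An order that follows the product would be worse: the child's reaction to application would be on tape in some arms and missing in others, and the pre-period contrast would partly reflect when the camera started. This matters because the hypothesis (1.2) relies on independent observation, and the primary outcome (2.1) covers anxiety as well as pain. Of the two scales described in 3.1, only the PBCL rates anxiety.

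The 'before' FPS-R raises a separate timing question. The trial is open label (4.1) and its outcome is worded as a reduction (2.1), so the first score may be read as a baseline. As written, it could be taken once the arm is known or the intervention is already on the skin.

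**Working it through.** No effect size can be computed from the documents. The check sets the windows side by side and counts who could be affected.

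**1. Windows**

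| | Start | End |
|---|---|---|
| Tape (10.1) | Sterilization | Completion of venipuncture |
| PBCL pre-period (17.1) | Not stated; at or before placement | Needle insertion |
| PBCL procedure period (17.1) | Needle insertion | Needle withdrawal |

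The tape secures the whole pre-period only if that period begins no earlier than sterilization. Since the period must contain placement, this requires placement to follow sterilization in every child. Section 10.1 requires only that placement precede the needle. The procedure period falls after sterilization whatever the order, so this gap does not reach it.

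**2. Children affected.** Inputs from 5.1: 56 per arm, and 3 × 56 = 168. Assumption: full enrolment and one order within each arm.

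| Arms with placement before cleaning | Placement off tape | Pairwise contrasts with unequal pre-periods |
|---|---|---|
| None | 0 | None |
| Any one arm | 56 | That arm against each of the other two |
| Any two arms | 56 + 56 = 112 | Each of those two against the third |
| All three | 168 | None, but placement is unscored throughout |

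If the order varies from child to child, any number from 0 to 168 is possible.

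**3. One example.** Suppose Buzzy and the sham band go on before cleaning and the spray after it. Then 112 children have placement off tape and the 56 in the vapocoolant arm do not. Buzzy and sham are cut at the same point, so their contrast has no unequal start. Only the two contrasts with vapocoolant are affected. Section 3.1 cites the hypothesis that children feel cold on the skin as painful. If spraying provokes distress that the checklist picks up, vapocoolant would look worse in the pre-period. A different order would change which contrasts are affected, and possibly the direction.

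**4. FPS-R.** The stated sequence is consent, randomization, intervention, needle. A form completed before the venipuncture fits anywhere ahead of the needle, including after the second or third step.

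**The case against.** The best reply is that this is under-specification, not a demonstrated conflict. If every intervention follows skin cleaning, 10.1 and 17.1 agree and nothing is lost. The nurse training videos (10.1), the device instructions (21.2) or the data form may settle the order. That stands as a limit: the claim is only that the protocol text does not secure the footage.

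Other limits also stand:

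- A reader might infer that the pre-period starts with placement. Section 17.1 says only that placement is included. The start is undefined, so the gap is the same or wider.
- A reader might infer that 112 children lose their placement footage and that the pre-period favors Buzzy and sham whatever their true effects. The documents state no order. The inference also needs a reaction that ends before cleaning: if a device or band stays on, a continuing reaction would be filmed. Buzzy's ice wings are cold too.
- Separate scores by period appear only in the analysis text. Section 18.1 A speaks of one score per subject, so a distinct pre-period score is itself not fully settled.
- The FPS-R timing is a different issue from the camera. Section 17.1 specifies no change-from-baseline or baseline-adjusted analysis, so harm from a contaminated baseline is conditional on such use.

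None of this closes the gap between what is taped and what is to be scored.

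**Conclusion.** The point holds in limited form. The taping rule does not guarantee footage of the pre-period that the analysis defines. Between 0 and 168 children could be affected, depending on an order the protocol does not give. Bias between arms arises only if that order differs by arm, and then only in pre-period contrasts between an arm whose placement is filmed and one whose placement is not. Its size cannot be computed, and its direction is not fixed by the documents. This rests on the video being the sole source of PBCL scores, which is how the protocol describes it.

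The FPS-R point stands separately: the timing of the 'before' form is open. The text does not show that it will be taken after allocation.

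The end of the tape is another matter. "Post-procedure is defined as the 2 minute time period after needle withdrawal", which also appears to lie beyond the recording, but correcting that would leave the start unresolved.

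**What to change.** - **10.1, videotaping:** start the camera in all three arms before the assigned intervention is applied.
- **17.1 and its repeat after section 32:** start PBCL pre-period scoring at that same event. Neither change need prescribe the order of application and sterilization.
- **10.1, pain scores:** collect the 'before' FPS-R from child and guardian after consent and before the allocation is opened.

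The cost is protocol wording and slightly more video per child to record and review, with no extra staff or patients. Starting the scored period at sterilization instead would also reconcile the two windows. It would, however, give up any placement done earlier, which 17.1 means to include, and leave the arms unequal if the order differs. The change should be made before enrolment.

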2.0 Scientific Endpoints

2.1 Describe the scientific endpoint(s), the main result or occurrence under study.

*NOTE: Scientific endpoints are outcomes defined before the study begins to determine whether the objectives of the study have been met and to draw conclusions from the data. Include primary and secondary endpoints. Some example endpoints are: reduction of symptoms, improvement in quality of life, or survival. Your response should **not** be a date.*

Response:

Our primary outcome is that Buzzy will have a greater degree of reduction of anxiety and pain levels compared to vapocoolant or placebo.

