3.0 Background

3.1 Provide the scientific or scholarly background, rationale, and significance of the research based on the existing literature and how it will contribute to existing knowledge. Describe any gaps in current knowledge. Include relevant preliminary findings or prior research by the investigator.

Response:

Among pediatric patients, phlebotomy and intravenous cannulation are two important sources of self-reported pain in the pediatric ED. Unmanaged needle stick pain has been associated with needle phobia, greater pain with future sticks; anxiety associated with other medical procedures, healthcare avoidance and increased adult pain sensitivity (Lunoe, 2014; Cohen 1997; Hamilton, 1995; Pate, 1996). Various methods have been proposed for management of acute pain associated with these medical procedures. Pharmacological methods include EMLA, lidocaine and ethyl chloride (vapocoolant). Behavioral methods such as information provision, distraction, sensory focusing, and cognitive behavioral therapy (CBT) have also been utilized (Blount, 2009). Optimization of pain control during phlebotomy and IV catheterization in the Pediatric ED is essential in an effort to avoid the aforementioned adverse effects of needle insertion. In the pediatric ED, quick acting methods are favored over those requiring time to act such as EMLA and CBT.

Vapocoolants, volatile refrigerated liquids such as ethyl chloride, are a frequent choice in many pediatric EDs, including our own, prior to phlebotomy or IV cannulation. Despite this, research has offered conflicting results as to their efficacy. Hogan and her colleagues conducted a systematic review of Vapocoolant in both children and adults and concluded that their "...results demonstrated that Vapocoolants are ineffective in children when compared to placebo or no treatment" (Hogan ,2014). Shah, Taddio & Rieder have hypothesized that the sensation of cold on their skin is perceived by children as painful (Shah, 2009).

Recently several labs have introduced hand held devices based on Melzack and Wall's Gait Control theory (Melzack 1965) which asserts that activation of non-nociceptive fibers can interfere with signals from pain fibers thereby inhibiting pain. This theory helps to explain why rubbing or massaging a painful area of skin can lessen the pain. One such device is the Buzzy.. The Buzzy is a vibrating palm-sized device with removable ice wings developed by MMJ Labs Atlanta, GA.

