4.0 Study Design

4.1 Describe and explain the study design (e.g. case-control, cross-sectional, ethnographic, experimental, interventional, longitudinal, observational).

Response:

This is a single-center, randomized, open label, placebo controlled clinical trial.

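### The first Faces Pain Scale score is not tied to a point before allocation or placement, so it is not guaranteed to be a true baseline

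*Combined protocol and SAP*

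**What the plan says.** Section 10.1 gives three timings, under topic headings and not as a timed schedule.

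- Randomisation: "After obtaining informed consent, the patients will be randomized into one of the three groups following a randomization table created by a statistician".
- Intervention: "Whichever intervention is randomly selected will be performed on patient prior to the needle stick".
- FPS-R, by child and by guardian: "Before and after the venipuncture procedure, we will ask the legal guardian and subject to complete a Faces pain scale revised form".

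The same section has the video run over the whole procedure, "starting from sterilization and ending at the time when the venipuncture is completed".

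Four other places bear on the point.

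- Section 4.1 on blinding: "This is a single-center, randomized, open label, placebo controlled clinical trial".
- Section 2.1 on the endpoint: "Our primary outcome is that Buzzy will have a greater degree of reduction of anxiety and pain levels compared to vapocoolant or placebo".
- Section 17.1 defines a pre-procedure period for the observer checklist (PBCL), "including the placement of Vapocoolant, pain control or sham device up to needle insertion". It defines no such period for the FPS-R. It assigns pain scores to ANOVA without saying whether the outcome is the after-score, a change, or an after-score adjusted for the before-score.
- Section 3.1 reports, as a hypothesis raised by cited authors about vapocoolants, that "the sensation of cold on their skin is perceived by children as painful".

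**The concern.** A baseline should be measured before anything that differs between arms can influence it. Here the only stated limit on the first FPS-R is that it precedes the venipuncture. A research assistant who hands out the form after the allocation is known has followed Section 10.1. On one reading, so has an assistant who does so with the spray, ice wings or band already on.

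Two things could then move the score by arm. Child and guardian may rate differently because they know what the child has been given. If the score follows placement, the intervention may itself change what the child feels: upward if cold is unpleasant, downward if the device calms or distracts.

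The before-score is the only self-reported reference level in the trial, and the endpoint is a reduction. A before-score raised in one arm makes that arm's reduction look larger than it is; a lowered one hides a real benefit. If the moment of measurement also varies between patients or arms, the score does not measure the same thing throughout. None of this can be repaired once the data are collected.

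**Working it through.** **The plan's own figure.** Section 17.2 gives 168 subjects for a chi-square test with effect size w = 0.3, 8 degrees of freedom, alpha 0.05 and 80% power. With noncentrality N × w², the smallest N reaching 80% is 167, or 168 in equal thirds, with power 80.3% at 168. The figure reproduces. It has no bearing on the timing question beyond supplying 56 per arm.

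**What the text fixes.**

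| Event | Anchor stated | Order relative to the first FPS-R |
|---|---|---|
| Randomisation | after consent | not stated |
| Placement of intervention | before the needle stick | not stated |
| Start of taping | sterilization | not stated directly |
| First FPS-R | before the venipuncture procedure | – |

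Consent, FPS-R, randomisation, placement fits this table. So does consent, randomisation, FPS-R, placement. Consent, randomisation, placement, FPS-R fits if the venipuncture procedure is taken to begin with the needle.

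**Size if the score is shifted (illustration).** The documents give no FPS-R standard deviation, no before-after correlation and no shift. Assumed: SD from 2.5 to 3.5 points, correlation r from 0.3 to 0.5, and a shift d in the before-score of one arm of a pairwise comparison. The after-score is unaffected and there is no true effect. Normal approximation, two-sided 5%, n = 56 per arm, √(2/56) = 0.189.

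*Change score.* The bias is d. The standard error is SD × √(2(1 − r)) × 0.189.

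- SD 3.5, r 0.3, d = 1: 4.141 × 0.189 = 0.783; z = 1/0.783 = 1.28; rejection 24.8%.
- SD 2.5, r 0.5, d = 1: 2.5 × 0.189 = 0.472; z = 1/0.472 = 2.12; rejection 56.2%.

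*Adjustment for the before-score (ANCOVA).* The bias is r × d. The standard error is approximately SD × √(1 − r²) × 0.189.

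- SD 3.5, r 0.3, d = 1: 3.339 × 0.189 = 0.631; z = 0.3/0.631 = 0.475; rejection 7.6%.
- SD 2.5, r 0.5, d = 1: 2.165 × 0.189 = 0.409; z = 0.5/0.409 = 1.22; rejection 23.1%.

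This approximation ignores the small variance inflation caused by the baseline imbalance. Simulating the ANCOVA test at the same two corners gives about 7% and 22%.

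*After-score only.* The before-score does not enter, so rejection stays at 5%.

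| Shift in before-score | Change score | ANCOVA | After-score only |
|---|---|---|---|
| 0.5 point | 10–19% | 6–9% | 5% |
| 1 point (half a face) | 25–56% | 8–23% | 5% |

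**The opposite direction.** Suppose the intervention truly lowers the after-score by 1.5 points but has also lowered the before-score by 1. The expected change-score difference is 1.5 − 1 = 0.5. At SD 3.5, r 0.3, power falls from 48% (z = 1.5/0.783) to 10% (z = 0.5/0.783). At SD 2.5, r 0.5, it falls from 89% (z = 1.5/0.472) to 19% (z = 0.5/0.472).

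**The case against.** **Placement may come after the first score.** Section 10.1 has the tape of the venipuncture procedure start at sterilization. The PBCL is scored from that tape, and Section 17.1 puts placement inside the PBCL pre-procedure period. If placement is on tape, it happens at or after sterilization, and a score taken before the procedure precedes it. This reading is plausible and weakens the case that cold is already on the skin. It does not settle the matter: the windows are not well aligned, since the tape is stated to stop when the venipuncture is completed while the PBCL post period runs 2 minutes beyond needle withdrawal. It also says nothing about whether the arm is already known.

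**Section 10.1 does not state a late score.** A reader might infer from its order of topics that the first FPS-R is taken after open-label randomisation. The documents do not support that as fact. The FPS-R paragraph also follows the videotaping paragraph, although the first score clearly cannot follow the taping. A score between consent and randomisation fits equally well.

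**The plan names no analysis that would carry the bias.** Section 17.1 says ANOVA and mentions neither change scores nor adjustment, and the reduction in Section 2.1 can be read as a contrast between arms. This stands as a limit on the figures. It does not remove the concern, because the before-score is collected, the endpoint wording invites its use, and its role is left open.

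**The cold-pain premise is thin.** Section 3.1 reports a hypothesis about vapocoolant. Extending it to the ice wings, with an equal shift in both cold arms, is not supported. The calculation above needs only some arm-specific shift, of either sign.

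**Smaller points.** Section 17.1 limits the scores used to those of patient and observer, so the guardian's score may never be analysed, although Section 1.2 names parent report in the hypothesis. The data collection form and staff training may fix the timing; they are not among the documents reviewed.

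**Conclusion.** The point holds as a gap that permits bias, not as a demonstrated one. Section 10.1 ties the first FPS-R only to the venipuncture. A fully compliant score may therefore be taken after the arm is known, and possibly after placement, and nothing elsewhere in the documents rules this out. The score is not guaranteed to be a true baseline.

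The bias arises only if three things coincide: the score is taken after the arm is known or the intervention is on, it shifts by arm, and it then enters the analysis by subtraction or adjustment. Under the assumptions stated, a 1-point shift would raise the 5% error rate to about 25–56% for a change score and 8–23% for an adjusted analysis; with 0.5 point, to 10–19% and 6–9%. These ranges rest on an assumed SD, correlation and shift and are not forecasts for this trial. A reader might infer that the planned ANOVA is itself invalid; an ANOVA of the after-score alone is untouched by this problem.

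The change should be made: the remedy is small, and a contaminated before-score cannot be corrected later.

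**What to change.** **Section 10.1.** Require the first FPS-R, by child and by guardian, after consent and assent and before the allocation is revealed or anything is applied to the child. Record the clock time of that score and of the opening of the allocation. State that only a score taken in that window counts as baseline.

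**Section 17.1, and the same text repeated after Section 32.** State the role of the before-score. One suitable choice is the post-procedure FPS-R analysed by ANCOVA with arm as factor and the pre-allocation score as covariate. If the after-score alone is intended, say so, and describe the before-score as descriptive. Say also whether the guardian's scores are analysed.

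**Cost.** One sentence on order and one on analysis, plus two time fields on the data form. Forms, staff, visit and the sample size of 168 stay as they are.
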